Inotuzumab

B1931024 NON-INTERVENTIONAL STUDY PROTOCOL

Amended 8, 12 December 2023

BESPONSA® Injection 1 mg Special Investigation FULL PROTOCOL

Pfizer Japan Inc.

This document contains confidential information belonging to Pfizer. Except as otherwise agreed to in writing, by accepting or reviewing this document, you agree to hold this information in confidence and not copy or disclose it to others (except where required by applicable law) or use it for unauthorized purposes. In the event of any actual or suspected breach of this obligation, Pfizer must be promptly notified.

PFIZER CONFIDENTIAL

CT24-WI-JPN-GPSP01-RF09 8.0 Non-Interventional Study Protocol Template for Secondary Data Collection
Study 01-Nov-2023
Page 1 of 33

Inotuzumab

B1931024 NON-INTERVENTIONAL STUDY PROTOCOL

Amended 8, 12 December 2023

STUDY INFORMATION

Title	BESPONSA® Injection 1 mg Special Investigation
Protocol number	B1931024
Protocol version identifier	Amended 8
Date	12 December 2023
Active substance	Inotuzumab ozogamicin (genetical recombination)
Medicinal product	BESPONSA® Injection 1 mg
Research question and objectives	
The following matters will be investigated in patients receiving BESPONSA under actual conditions of use after marketing:
 
① Occurrence of adverse events (AEs) (including the following evaluations): Background characteristics possibly affecting the onset of liver disorder including venoocclusive liver disease (VOD)/sinusoidal obstruction syndrome (SOS), myelosuppression, infections and haemorrhage, and grade ≥ 3 events based on the Common Terminology Criteria for Adverse Events (CTCAE) v4.0 as well as risk factors for early death of hematopoietic stem cell transplant (HSCT) patients after BESPONSA treatment
 
Efficacy (hematologic remission rate and survival)

Author	PPD PPD

Inotuzumab

B1931024 NON-INTERVENTIONAL STUDY PROTOCOL

Amended 8, 12 December 2023

2. LIST OF ABBREVIATIONS

Abbreviation	Definition
ADR	adverse drug reaction
AE	adverse event
ALL	acute lymphocytic leukemia
ALT	alanine aminotransferase
AL-P	alkaline phosphatase
ANC	absolute neutrophil count
AST	aspartate aminotransferase
BUN	blood urea nitrogen
CNS	central nervous system
CR	complete remission
CRF	case report form
CRi	complete remission with incomplete count recovery
CTCAE	Common Terminology Criteria for Adverse Events
EC	ethics committee
ECOG	Eastern Cooperative Oncology Group
EDC	electronic data capture
EDP	exposure during pregnancy
γ-GTP	gamma glutamyl transpeptidase
GOT	glutamic oxaloacetic transaminase
GPT	glutamic pyruvic transaminase
GVHD	graft versus host disease
HSCT	hematopoietic stem cell transplant
IRB	institutional review board
MHLW	Ministry of Health, Labour and Welfare
MRD	minimal residual disease
NIS	non-interventional study
PMDA	Pharmaceuticals and Medical Devices Agency
SAE	serious adverse event
SAP	statistical analysis plan
SOS	sinusoidal obstruction syndrome
ULN	upper limit of normal
VOD	venoocclusive disease
WHO	World Health Organization

Inotuzumab

B1931024 NON-INTERVENTIONAL STUDY PROTOCOL

Amended 8, 12 December 2023

4. AMENDMENTS AND UPDATES

Version Identifier	Date	Amendment Type (substantial or administrative)	Protocol Section(s) Changed	Summary of Amendment(s)	Reason
Amended 8	12 December 2023	Administrative revision	AMENDMENTS AND UPDATES	Addition of "Type of revision"	Change associated with the revision of the internal formats, amendment of the protocol
			LIST OF ABBREVIATIONS	Adjustment of description	Change associated with the revision of the internal formats
		Substantial revision	Planned Study Period	Change of the registration period	Because registration not necessitating creation of CRFs is terminated based on Q&A5 of Administrative Notice dated 10 August 2023.
			Study Method	Correction of description about "registration-only investigation"	
			Patient Registration	Deletion of description about "registration-only investigation"	
		Administrative revision	PLANS FOR DISSEMINATING AND COMMUNICATING STUDY RESULTS	Adjustment of description	Change associated with the revision of the internal formats
			NAME, ADDRESS, AND OUTSOURCED OPERATIONS OF THE PERSON WHO WAS CONTRACTED WITH THE OPERATIONS	Addition of A2 Healthcare Corporation	Change of the outsource of EDC account management activities
Amended 7	11 November 2022	Administrative revision	Study information	Change from "Date of last version of protocol" to "Date of creation" Change of the division name of the author	Change associated with the revision of the internal formats, change of the organization
			LIST OF ABBREVIATIONS	Addition of items, adjustment of description	Change associated with the revision of the internal formats
			RESPONSIBLE PARTIES	Deletion of "Clinical Lead (group head)"	Change associated with the revision of the internal formats, amendment of the protocol
			AMENDMENTS AND UPDATES	Deletion of "Amendment of the	Change associated with the revision of the internal formats,

PFIZER CONFIDENTIAL

CT24-WI-JPN-GPSP01-RF09 8.0 Non-Interventional Study Protocol Template for Secondary Data Collection

Study 01-Nov-2023

Page 8 of 33

Inotuzumab

B1931024 NON-INTERVENTIONAL STUDY PROTOCOL

Amended 8, 12 December 2023

090177e1a24e51ba\Approved\Approved On: 03-Dec-2024 06:33 (GMT)

				Plan/Others," addition of the amendment	amendment of the protocol
			MILESTONES	Addition of items, postponement of the date of final report preparation	Change associated with the revision of the internal formats, delay of the investigation
			Data analysis Limitations of the research methods PLANS FOR DISSEMINATING AND COMMUNICATING STUDY RESULTS	Adjustment of description	Change associated with the revision of the internal formats
			MANAGEMENT AND REPORTING OF ADVERSE EVENTS/ADVERSE DRUG REACTIONS	Change of terms, adjustment of description	Change associated with the revision of the internal formats
			COMMUNICATION OF ISSUES ORGANIZATIONAL SYSTEM FOR STUDY IMPLEMENTATION	Deletion	Change associated with the revision of the internal formats
			NAME, ADDRESS AND OUTSOURCED OPERATIONS OF THE PERSON WHO WAS CONTRACTED WITH THE OPERATIONS	Addition of "Monitoring" to Pfizer R&D Japan G.K.	Expansion of the scope of outsourcing
			CONTACT INFORMATION	Changes of the organization name of Pfizer R&D Japan G.K. and the name, telephone number, and e-mail address of the contact information for the EDC system	Change of the organization, change of the contact information for the EDC system
Amended 6.1	8 June 2022	Administrative revision	Cover page	Change of the company logo	Change of the logo
Amended 6	22 April 2020	Substantial revision	Duration of study	Change of the registration period	Moving on to a patient registration-only investigation
			Study procedures	Description of the moving on to a patient registration-only investigation	
			Observation period	Description of a patient from whom data should be	

PFIZER CONFIDENTIAL

CT24-WI-JPN-GPSP01-RF09 8.0 Non-Interventional Study Protocol Template for Secondary Data Collection

Study 01-Nov-2023

Page 9 of 33

Inotuzumab

B1931024 NON-INTERVENTIONAL STUDY PROTOCOL

Amended 8, 12 December 2023

090177e1a24e51ba\Approved\Approved On: 03-Dec-2024 06:33 (GMT)

				collected to the extent possible at the medical institution to which the patient has been transferred	
			Patient registration	Addition of the description of the moving on to a patient registration-only investigation	
Amended 5	22 May 2019	Administrative revision	Data management	Addition of the "Case report forms/Electronic data records" and "Record retention" sections	Change associated with the revision of the internal formats
			PROTECTION OF HUMAN SUBJECTS	Changes to the "Patient information," "Patient consent," and "Ethical conduct of the study" sections	
			Adverse events	Correction of description	
			Single reference safety document	Deletion	
			CONTACT INFORMATION	Change of the e-mail address in "the contact information for the EDC system"	Change of the e-mail address
			Overall	Unification of "Pfizer Japan Inc." to "Pfizer"	Unification of the term
Amended 4	1 December 2018	Administrative revision	NAME, ADDRESS, AND OUTSOURCED OPERATIONS OF THE PERSON WHO WAS CONTRACTED WITH THE OPERATIONS	Addition of Pfizer R&D Japan G.K.	Establishment of Pfizer R&D Japan G.K.
			CONTACT INFORMATION	Change of the name of the contact information for the contents of the study to "Pfizer R&D Japan G.K."	
Amended 3	25 May 2018	Administrative revision	Variables	Correction of errors in writing, adjustment of description	Errors in writing
			MANAGEMENT AND REPORTING OF ADVERSE EVENTS/ADVERSE DRUG REACTIONS	Adjustment of description	Accurate definition of the reporting period, reflection of the internal formats

PFIZER CONFIDENTIAL

CT24-WI-JPN-GPSP01-RF09 8.0 Non-Interventional Study Protocol Template for Secondary Data Collection

Study 01-Nov-2023

Page 10 of 33

Inotuzumab

B1931024 NON-INTERVENTIONAL STUDY PROTOCOL

Amended 8, 12 December 2023

Amended 2	29 March 2018	Administrative revision	NAME, ADDRESS, AND OUTSOURCED OPERATIONS OF THE PERSON WHO WAS CONTRACTED WITH THE OPERATIONS	Addition of EPS Corporation and Medidata Solutions K.K.	Determination of the contractors
			CONTACT INFORMATION	Addition of the contact information for the contents of the study and the contact information for the EDC system	Determination of the contact information
			Overall	Adjustment of description	Adjustment of description
Amended 1	14 March 2018	Substantial revision	Variables	(1) Background: Addition of "Date of confirming the initial onset" as an item not to be collected for transferred patients. (2) Clinical laboratory tests: Addition of peripheral blast cells and myeloblast cells	(1) Omission of description (2) Addition of the parameters to investigate risk factors
First version	7 March 2018	N/A	N/A	N/A	N/A

5. MILESTONES

Milestone	Planned date
Start of investigation period	Start date of releasing BESONSA to the market
Start of data collection (registration date of the first patient)	2 July 2018
End of investigation period	5 years after the start date of releasing BESONSA to the market*
End of data collection (release date of the database)	May 2024
Final study report	October 2024

*: See Section 8.4. "Planned Study Period."

6. RATIONALE AND BACKGROUND

BESONSA® Injection 1 mg (nonproprietary name, inotuzumab ozogamicin [genetical recombination]) (hereinafter referred to as BESONSA) is a chemotherapeutic targeting the CD22 antigen that is an antibody-drug conjugate composed of a CD22-specific antibody linked to calicheamicin, a cytotoxic antitumor antibiotic. In Japan, the drug was approved in January 2018 for the indication, "Relapsed or refractory CD22-positive acute lymphoblastic leukemia (ALL)."

PFIZER CONFIDENTIAL

CT24-WI-JPN-GPSP01-RF09 8.0 Non-Interventional Study Protocol Template for Secondary Data Collection

Study 01-Nov-2023

Page 11 of 33

Inotuzumab

B1931024 NON-INTERVENTIONAL STUDY PROTOCOL

Amended 8, 12 December 2023

The “BESPONSA® Injection 1 mg Special Investigation” will be conducted to understand the safety of BESPONSA when administered under actual conditions of use in ALL patients.

7. RESEARCH QUESTION AND OBJECTIVES

7.1. Safety Specifications

7.1.1. Important Identified Risks

(1) Liver disorder including venoocclusive liver disease (VOD)/sinusoidal obstruction syndrome (SOS)*

Rationale: In global Phase 3 (B1931022) and non-Japanese Phase 1/2 (B1931010) studies in patients with relapsed or refractory ALL, VOD/SOS frequently occurred, and grade ≥ 3 hepatotoxicity was also reported in the inotuzumab ozogamicin group. Hence, the occurrence of adverse drug reactions (ADRs) and other relevant matters after marketing will be examined in the special investigation.

(2) Myelosuppression

Rationale: In Study B1931022, myelosuppression occurred in the inotuzumab ozogamicin group, and many of these events were grade ≥ 3 . Hence, the occurrence of ADRs and other relevant matters after marketing will be evaluated in the special investigation.

(3) Infections

Rationale: In Study B1931022, infections occurred in many patients in the inotuzumab ozogamicin group, and infections attributable to myelosuppression would be likely to frequently develop. Hence, the occurrence of ADRs and other relevant matters after marketing will be assessed in the special investigation.

(4) Hemorrhage

Rationale: In Study B1931022, hemorrhage occurred in the inotuzumab ozogamicin group, and hemorrhage attributable to myelosuppression would be likely to frequently develop. Hence, the occurrence of ADRs and other relevant matters after marketing will be examined in the special investigation.

(5) Tumor lysis syndrome

Rationale: In Study B1931022, tumor lysis syndrome occurred in the inotuzumab ozogamicin group, and many of these events were grade ≥ 3 . Hence, the occurrence of ADRs and other relevant matters after marketing will be evaluated in the special investigation.

(6) Infusion reaction

Rationale: In Study B1931022, infusion reaction related to inotuzumab ozogamicin occurred in the inotuzumab ozogamicin group. Hence, the occurrence of ADRs and other relevant matters after marketing will be assessed in the special investigation.

(7) Pancreatitis

Rationale: In Studies B1931022 and B1931010, and Studies B1931006 and B1931008 involving subjects other than patients with relapsed or refractory ALL, pancreatitis occurred in the inotuzumab ozogamicin group. Pancreatitis may affect the benefit-risk balance of inotuzumab ozogamicin.

PFIZER CONFIDENTIAL

CT24-WI-JPN-GPSP01-RF09 8.0 Non-Interventional Study Protocol Template for Secondary Data Collection

Study 01-Nov-2023

Page 12 of 33

Inotuzumab

B1931024 NON-INTERVENTIONAL STUDY PROTOCOL

Amended 8, 12 December 2023

Hence, the occurrence of ADRs and other relevant matters after marketing will be examined in the special investigation.

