7.2. Research Objectives

The following matters will be investigated in patients receiving BESPONSA under actual conditions of use after marketing:

(1) Occurrence of adverse events (AEs) (including the following evaluations):

Background characteristics possibly affecting the onset of liver disorder including VOD/SOS, myelosuppression, infections and hemorrhage, and grade ≥ 3 events based on the CTCAE v4.0 as well as risk factors for early death of HSCT patients after BESPONSA treatment

(2) Efficacy (hematologic remission rate and survival)

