8.8.8. Clinical Laboratory Tests

- (1) Hematology (red blood cell count, hemoglobin, hematocrit, white blood cell count, differential white blood count, peripheral blast cells and platelet count)
- (2) Hepatic function test (AST [GOT]*, ALT [GPT]*, AL-P, γ-GTP, total bilirubin*)

*: Data on the upper limit of normal (ULN) at the site will be entered.

- (3) Renal function test (BUN, creatinine)
- (4) Electrocardiography (QT, QTc)

PFIZER CONFIDENTIAL

CT24-WI-JPN-GPSP01-RF09 8.0 Non-Interventional Study Protocol Template for Secondary Data Collection
Study 01-Nov-2023

Inotuzumab

B1931024 NON-INTERVENTIONAL STUDY PROTOCOL

Amended 8, 12 December 2023

(5) Pancreatic function test (amylase, lipase)

(6) Bone marrow test (myeloblast)

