- White blood cell count immediately before the start of this drug [ $\leq 4000/\text{mm}^3$ ,  $\geq 4000/\text{mm}^3$ , not performed]
- Neutrophil count immediately before the start of this drug [ $\leq 2000/\text{mm}^3$ ,  $\geq 2000/\text{mm}^3$ , not performed]
- Platelet count immediately before the start of this drug [ $< 10 \times 10^4/\mu\text{L}$ ,  $\geq 10 \times 10^4/\mu\text{L}$ , not performed]
- Peripheral blast count immediately before the start of this drug [ $\leq 1000/\mu\text{L}$ ,  $> 1000/\mu\text{L}$ , not performed]
- Myeloblast count immediately before the start of this drug [ $\leq 50\%$ ,  $> 50\%$ , not performed]
- Salvage line of the induction treatment with this drug [Initial induction, 1st, 2nd, 3rd or later]
- HSCT before the start of this drug [not performed, performed]

Subgroup analyses of safety will be performed also for the following factors:

- HSCT after the start of this drug [not performed, performed]
- Type of the first HSCT after the start of this drug [autologous transplant, allogeneic hematopoietic stem cell transplant with myeloablative conditioning, allogeneic hematopoietic stem cell transplant with nonmyeloablative conditioning, unknown]
- Donor of the first HSCT after the start of this drug [alternative donor, matched related donor]
- Conditioning with alkylating agent for the first HSCT after the start of this drug [ $\leq 1$  agent (including no conditioning),  $\geq 2$  agents]
- Conditioning with busulfan for the first HSCT after the start of this drug [not performed (including no conditioning), performed]
- ECOG PS before conditioning for the first HSCT after the start of this drug [0, 1,  $\geq 2$ , not performed]
- AST and ALT levels before conditioning for the first HSCT after the start of this drug [ $\leq 1.5 \times$  the institutional upper limit of normal range (IULN), either  $> 1.5 \times$  IULN, not performed]
- $\gamma$ -GTP level before conditioning for the first HSCT after the start of this drug [ $\leq 50$  IU/L,  $> 50$  IU/L, not performed]

- Total bilirubin level before conditioning for the first HSCT after the start of this drug [≤ institutional upper limit of normal range (IULN), > IULN, not performed]
- Hemoglobin level before conditioning for the first HSCT after the start of this drug [< 10 g/dL, ≥ 10 g/dL, not performed]
- Platelet count before conditioning for the first HSCT after the start of this drug [< 10 × 10^4/µL, ≥ 10 × 10^4/µL, not performed]

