- Age [< 15 years,  $\geq 15$  to  $< 65$  years,  $\geq 65$  years]
- Age [< 18 years,  $\geq 18$  to  $< 55$  years,  $\geq 55$  years]
- Age [< 15 years,  $\geq 15$  to  $< 40$  years,  $\geq 40$  years]
- Hepatic impairment
- Renal impairment
- HSCT before the start of this drug
- Total dose per cycle  $> 1.8$  mg/m^2
- Pregnancy \* Pregnancy during the treatment period. Limited to cases in which information on pregnancy is collected

Similarly, ADRs meeting definition of liver disorder including safety specification events of VOD/SOS will be analyzed by each of the following factors. Similar analyses will also be performed for ADRs of Grade 3 or higher based on CTCAE v4.0.

- Age [< 15 years,  $\geq 15$  to  $< 65$  years,  $\geq 65$  years]
- Age [< 18 years,  $\geq 18$  to  $< 55$  years,  $\geq 55$  years]
- Age [< 15 years,  $\geq 15$  to  $< 40$  years,  $\geq 40$  years]
- Hepatic impairment
- Medical history (past) - VOD/SOS
- Medical history (past) - Hepatitis or hepatic disease
- Medical history (present) - VOD/SOS
- Medical history (present) - Hepatitis or hepatic disease
- ECOG PS before the start of this drug

- AST and ALT levels immediately before the start of this drug
- $\gamma$ -GTP level immediately before the start of this drug
- Total bilirubin level immediately before the start of this drug
- Platelet count immediately before the start of this drug
- Peripheral blast count immediately before the start of this drug
- Salvage line of the induction treatment with this drug
- HSCT before the start of this drug

Similarly, ADRs meeting definition of safety specification events of myelosuppression will be analyzed by each of the following factors. Similar analyses will also be performed for ADRs of Grade 3 or higher based on CTCAE v4.0.

- Age [ $< 15$  years,  $\geq 15$  to  $< 65$  years,  $\geq 65$  years]
- Age [ $< 18$  years,  $\geq 18$  to  $< 55$  years,  $\geq 55$  years]
- Age [ $< 15$  years,  $\geq 15$  to  $< 40$  years,  $\geq 40$  years]
- Hepatic impairment
- Renal impairment
- Total dose per cycle  $> 1.8 \text{ mg/m}^2$
- ECOG PS before the start of this drug
- White blood cell count immediately before the start of this drug
- Neutrophil count immediately before the start of this drug
- Platelet count immediately before the start of this drug
- Salvage line of the induction treatment with this drug
- HSCT before the start of this drug

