Similarly, ADRs meeting definition of safety specification events of infection will be analyzed by each of the following factors. Similar analyses will also be performed for ADRs of Grade 3 or higher based on CTCAE v4.0.

- Age [ $< 15$  years,  $\geq 15$  to  $< 65$  years,  $\geq 65$  years]
- Age [ $< 18$  years,  $\geq 18$  to  $< 55$  years,  $\geq 55$  years]
- Age [ $< 15$  years,  $\geq 15$  to  $< 40$  years,  $\geq 40$  years]
- Hepatic impairment
- Renal impairment
- Total dose per cycle  $> 1.8 \text{ mg/m}^2$
- ECOG PS before the start of this drug
- Salvage line of the induction treatment with this drug
- HSCT before the start of this drug

Similarly, ADRs meeting definition of safety specification events of hemorrhage will be analyzed by each of the following factors. Similar analyses will also be performed for ADRs of Grade 3 or higher based on CTCAE v4.0.

- Age [ $< 15$  years,  $\geq 15$  to  $< 65$  years,  $\geq 65$  years]
- Age [ $< 18$  years,  $\geq 18$  to  $< 55$  years,  $\geq 55$  years]

- Age [ $< 15$  years,  $\geq 15$  to  $< 40$  years,  $\geq 40$  years]
- Hepatic impairment
- Renal impairment
- Total dose per cycle  $> 1.8 \text{ mg/m}^2$
- ECOG PS before the start of this drug
- Salvage line of the induction treatment with this drug
- HSCT before the start of this drug

Similarly, patients who experienced GVHD will be analyzed by each of the following factors. GVHD events included in the analysis will be events of which PT includes GVHD according to the version of MedDRA used for the analysis.

- Medical history (past) - GVHD
- Medical history (present) - GVHD

Similar analyses will be performed for serious ADRs.

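### No prespecified analysis relates baseline neutrophil or white cell count to infection ADRs, or baseline platelet count to hemorrhage ADRs, although background factors for both risks are a stated objective

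*Protocol*

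**What the plan says.** Protocol 7.1.1 gives the reason for following two of the identified risks: "infections attributable to myelosuppression would be likely to frequently develop" and "hemorrhage attributable to myelosuppression would be likely to frequently develop". Protocol 7.2, objective (1), repeated in SAP 2.2, asks about "Background characteristics possibly affecting the onset of liver disorder including VOD/SOS, myelosuppression, infections and hemorrhage".

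The data exist. Protocol 8.8.8 lists "differential white blood count, peripheral blast cells and platelet count" among the hematology items. SAP 5.4 defines classes for white blood cell, neutrophil and platelet counts before treatment as safety subgroup factors (for example "Platelet count immediately before the start of this drug").

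SAP 8.2.3.4 then selects factors outcome by outcome. The myelosuppression list includes "Neutrophil count immediately before the start of this drug" together with white cells and platelets. For the other two risks it states that "ADRs meeting definition of safety specification events of infection will be analyzed by each of the following factors" and "ADRs meeting definition of safety specification events of hemorrhage will be analyzed by each of the following factors". Those two lists are the same: three age groupings, hepatic impairment, renal impairment, dose per cycle above 1.8 mg/m², ECOG PS, salvage line and prior HSCT. Each is run for all grades and for Grade 3 or higher.

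**The concern.** The plan sets out to find which patient characteristics go with infection and hemorrhage, and it gives myelosuppression as a route to both. A patient's neutrophil or platelet reserve before the first dose is a natural background characteristic to examine, and the SAP already treats it as relevant to myelosuppression itself. Leaving it out of the two downstream risks means that the planned tables will be silent on whether patients who start with low counts have more infections or more bleeding. Anyone who asks will need an unplanned analysis. SAP 8.2.3.5 permits one, but names none and reports results only where they are judged important to interpretation, so a null result could go unreported.

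**Working it through.** **Where baseline counts enter the planned safety factor analyses**

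| Outcome | SAP section | Neutrophils | White cells | Platelets |
|---|---|---|---|---|
| VOD/SOS | 8.2.3.1 | no | no | yes |
| Early death after HSCT | 8.2.3.3 | no | no | yes |
| Any ADR | 8.2.3.4 | no | no | yes |
| ADRs by SOC and PT | 8.2.3.4 | no | no | no |
| Liver disorder | 8.2.3.4 | no | no | yes |
| Myelosuppression | 8.2.3.4 | yes | yes | yes |
| Infection | 8.2.3.4 | no | no | no |
| Hemorrhage | 8.2.3.4 | no | no | no |
| GVHD | 8.2.3.4 | no | no | no |

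Neutrophil and white cell counts are used for one outcome only. Platelets are used for five, and hemorrhage is not among them. SAP 6.4 names covariates for liver disorder, VOD/SOS, remission and survival, but none for infection or hemorrhage. The revision history shows that version 5.0 added the myelosuppression, infection and hemorrhage analyses together; it gives no reason for treating their factor lists differently.

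**Size of the gap**

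- Infection and hemorrhage lists: nine entries each. Three are age groupings, so 9 − 2 = 7 distinct factors. None is a blood count.
- Missing rows: 2 (infection) + 1 (hemorrhage) = 3.
- With all grades and Grade 3 or higher: 3 × 2 = 6 comparisons.

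**The plan's only power figure, and why it does not carry over**

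Inputs from Protocol 8.10.2: 176 patients split 1:1 (88 per group), overall incidence 12.3%, relative risk 3.0, two-sided level 0.1. The unrounded rates are 18.45% and 6.15%.

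- Pooled SE = √(2 × 0.123 × 0.877 / 88) = 0.0495
- Unpooled SE = √((0.1845 × 0.8155 + 0.0615 × 0.9385) / 88) = 0.0486
- Power = Φ((0.123 − 1.645 × 0.0495) / 0.0486) = Φ(0.854) = 80.4%, as stated

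This is a VOD/SOS calculation by chi-square. The documents give no incidence for infection or hemorrhage. SAP 8.1.3 makes Fisher's exact test the default for nominal factors, and exact power with the same inputs is 75.2%.

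**Could the added rows be informative?**

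Illustration only. The event rates, relative risks and low-count shares are assumptions. With 176 patients, a two-sided level of 0.1, the chi-square approximation and 30% to 70% of patients with a low count:

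| Event rate | Relative risk | Power |
|---|---|---|
| 20% | 1.5 | 29% to 38% |
| 20% | 2.0 | 56% to 74% |
| 30% | 2.0 | 78% to 91% |
| 50% | 1.5 | 73% to 85% |

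For low rate p in the normal-count group and share s with low counts, p = overall rate / (s × RR + 1 − s). Fisher's test, and patients in the class for tests not done, would lower these values. The rows could be useful unless both the event rate and the effect are small.

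**Classes to be reused**

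In SAP 5.4 the neutrophil classes read ≤ 2000 and ≥ 2000, and the white cell classes ≤ 4000 and ≥ 4000, so a value on the boundary falls in both. That section underlines its reference categories, and an underlined less-than sign can look like ≤, so the formatted SAP should be checked. The platelet classes do not overlap.

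**The case against.** The strongest reply is that the protocol's rationale concerns myelosuppression arising under treatment, not counts before the first dose. That is right: the rationale does not name baseline counts, and there is no contradiction between protocol and SAP. What remains is that the objective asks about background characteristics and the SAP itself uses baseline counts as such for myelosuppression.

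It can also be said that SAP 5.4 already lists the counts for safety in general. But 8.2.3.4 selects from that list for each outcome, and for these two it does not select them.

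All testing is exploratory (SAP 4.1) and further analyses are allowed (SAP 8.2.3.5). Both points stand and lower the consequence. The accurate description is that the analysis is not prespecified, not that it can never be made.

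A reader might infer that salvage line or ECOG PS will show ratios that really belong to low counts, and that the added rows would cure this. Suppose risk is 18.45% with low and 6.15% with normal counts, and low counts occur in 70% of later-line and 40% of first-salvage patients (all assumed for these outcomes). Salvage line with no effect of its own then shows (0.7 × 0.1845 + 0.3 × 0.0615) / (0.4 × 0.1845 + 0.6 × 0.0615) = 0.1476 / 0.1107 = 1.33. The documents give no such splits, and one-factor rows would leave that 1.33 unchanged. Protocol 8.14 already concedes that confounding may not be adequately handled.

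**Conclusion.** The gap is real and can be confirmed from the factor lists alone. For two of the four risks named in the objective, the planned tables omit baseline counts that are collected, classed and used elsewhere in the same section. It is a cheap improvement to an exploratory analysis; no planned estimate is wrong because of it.

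Two stronger conclusions might be drawn and are not supported. One is that the study cannot answer its question on infection and hemorrhage: seven other factors are analyzed for each, at two grade levels, so the objective is addressed with one kind of candidate factor missing. The other is that the missing comparisons would have the design's 80.4% power: that figure rests on VOD/SOS incidence and effect size. The conclusion assumes only that baseline counts are a reasonable background factor for these risks, which the protocol's expectation of events through myelosuppression supports but does not prove.

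**What to change.** In SAP 8.2.3.4:

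- add the neutrophil count and the white blood cell count before the start of treatment to the infection list;
- add the platelet count before the start of treatment to the hemorrhage list;
- apply each to all grades and to Grade 3 or higher, with the SAP 8.1.3 risk ratios and tests.

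In SAP 5.4, make the neutrophil and white cell classes mutually exclusive, so that 2000 and 4000 each fall in one class only. If the final analysis has already been run, produce the rows from the existing database and label them as added. State beside the tables that the ratios are crude and that salvage line, ECOG PS and prior HSCT are not adjusted for baseline counts.

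Cost: no new data and no new factors. There are six more exploratory comparisons in the safety analysis set, or 3 × 3 = 9 if the closing sentence of 8.2.3.4 on serious ADRs is taken to cover these lists. Repeating them in the set with informed consent would double either number, to 12 or 18.
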